9.2.2.3 Conditions Not Requiring Dose Reduction

The following conditions are exceptions to the above guidelines. Carfilzomib, lenalidomide, and dexamethasone do not need to be held in the following cases:

- Grade 3 nausea, vomiting, or diarrhea (unless persisting more than 3 days with adequate treatment of antiemetics or antidiarrheal agents)
- Grade 3 dexamethasone-related hyperglycemia
- Grade 3 fatigue (unless persisting for > 14 days)
- Alopecia

9.2.3 *DEXAMETHASONE DOSE MODIFICATION GUIDELINES*

Two dose reduction levels are defined for dexamethasone, as illustrated in [Table 10](#) below:

Table 10 Dose Decrments for Dexamethasone

Nominal Dose (mg)	Reduced Dexamethasone Doses (mg)	
	Dose -1	Dose -2
40	20	12

Dexamethasone will be permanently discontinued after 2 dose reductions in the event of additional dexamethasone-related toxicities. At the investigator's discretion, dexamethasone may be tapered prior to complete discontinuation according to institutional practice. The subject may continue on treatment with the other protocol-specified drug(s). Guidelines for dexamethasone dose modifications are summarized in [Table 11](#).

Table 11 Treatment Guidelines for Dexamethasone-related Toxicity

Dexamethasone-related Toxicities, All Days and Cycles		
Symptom	Findings	Recommended Action
Cardiovascular	Edema > Grade 3 (anasarca or limiting function and unresponsive to therapy)	
 Diuretics as needed, and restart dexamethasone at 1 dose decrement; if edema persists despite above measures, decrease dose by another dose decrement. Discontinue dexamethasone permanently if symptoms persist despite second reduction.
Gastrointestinal Toxicity	Dyspepsia, gastric or duodenal ulcer, or gastritis Grade 1 or 2 (requiring medical management)	
 Continue dexamethasone at same dose and treat with therapeutic doses of histamine 2 (H2) blockers, or proton pump inhibitor. Consider adding sucralfate or other antiulcer treatment as clinically indicated. If symptoms persist despite above measures, decrease dexamethasone dose by 1 dose level.
	Dyspepsia, gastric or duodenal ulcer, or gastritis \geq Grade 3 (requiring hospitalization or surgery)	
 Hold dexamethasone until symptoms return to baseline. Restart dexamethasone at 1 dose decrement along with concurrent therapy with H2 blockers, sucralfate, or omeprazole. If symptoms persist despite above measures, discontinue dexamethasone permanently.
	Acute pancreatitis	
 Discontinue dexamethasone permanently.
General Disorders	Limb edema > Grade 3 ($> 30\%$ limb discrepancy in volume; gross deviation from normal anatomic contour; limiting self-care activities of daily living)	
 Hold dexamethasone until symptoms return to baseline. Diuretics as needed, and restart dexamethasone at 1 dose decrement; if edema persists despite above measures, decrease dose by another dose decrement. Discontinue dexamethasone permanently if symptoms persist despite second reduction.
Psychiatric Disorders	Confusion or mood alteration \geq Grade 2 (interfering with function \pm interfering with activities of daily living)	
 Hold dexamethasone until symptoms return to baseline. Restart dexamethasone at 1 dose decrement. If symptoms persist despite above measures, reduce by another dose decrement.
Musculoskeletal	Muscle weakness \geq Grade 2 (symptomatic and interfering with function \pm interfering with activities of daily living)	
 Decrease dexamethasone by 1 dose decrement. If weakness persists, decrease dose by another dose decrement. Discontinue dexamethasone permanently if symptoms persist.

Page 1 of 2

Table 11 Treatment Guidelines for Dexamethasone-related Toxicity (cont'd)

Dexamethasone-related Toxicities, All Days and Cycles		
Symptom	Findings	Recommended Action
Metabolism and Nutrition Disorders	Hyperglycemia \geq Grade 3 (fasting glucose > 250 mg /dL)	
Hold dexamethasone until glucose is \leq Grade 2 (< 250 mg/dL) and treat with insulin or other hypoglycemic agents as needed.If uncontrolled despite above measures, decrease dose by 1 dose decrement until \leq Grade 2 (< 250 mg /dL).
All Other	Other toxicity \geq Grade 3 felt related to dexamethasone	
Hold dexamethasone dose. Resume at 1 dose decrement when toxicity has resolved to \leq Grade 2.If toxicity recurs, hold dexamethasone dose until toxicity has resolved to \leq Grade 2 and resume dexamethasone dose by another dose decrement.If toxicity recurs despite 2 dose decrements, discontinue dexamethasone permanently.

Page 2 of 2

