- ^b In the event of a possible drug-related nonhematologic toxicity, the investigator should, to the best of his/her ability, assess its relationship to lenalidomide, carfilzomib, dexamethasone, or the combination of KRD to the extent possible. If both carfilzomib and lenalidomide are considered likely to be involved, then recommended actions for both should be instituted. For nonhematologic toxicity likely due to dexamethasone, refer to [Table 11](#) for treatment guidelines for dexamethasone-related toxicity.
- ^c For grade 3 hypertension, baseline refers to an average SBP < 140 mmHg or DBP < 90 mmHg on appropriate antihypertensive therapy.

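### Protocol Section 9.2.2.3 lets dexamethasone continue through Grade 3 dexamethasone-related hyperglycemia, while Table 11 recommends holding it; the line in 9.2.2.3 needs correcting

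*Protocol*

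**What the plan says.** Section 9.2.2.3 of the protocol lists conditions for which study drugs may continue. It opens with "The following conditions are exceptions to the above guidelines" and then says "Carfilzomib, lenalidomide, and dexamethasone do not need to be held in the following cases". One bullet is "Grade 3 dexamethasone-related hyperglycemia". The gastrointestinal and fatigue bullets in the same list each carry a condition under which the exception lapses; the hyperglycemia bullet carries none.

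Section 9.2.3 follows directly and deals with dexamethasone alone. It says "Two dose reduction levels are defined for dexamethasone" (Table 10: 40 mg to 20 mg, then to 12 mg) and names Table 11 as the guideline for dexamethasone modifications. The hyperglycemia row of Table 11 applies at Grade 3 or higher, defined by "fasting glucose > 250 mg /dL". Its first step begins "Hold dexamethasone until glucose is" Grade 2 or lower, with insulin or another hypoglycemic agent as needed. Its second step begins "If uncontrolled despite above measures, decrease dose by 1 dose decrement until" Grade 2 or lower is reached.

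Footnote b to Table 9 (Section 9.2.2.2) adds: "For nonhematologic toxicity likely due to dexamethasone, refer to" Table 11.

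**The concern.** The two places give opposite advice on the same drug for the same event at the same grade. Section 9.2.2.3 names both dexamethasone and dexamethasone-related hyperglycemia, so an investigator has some reason to stop reading there. That investigator could give the full 40 mg steroid dose at a Grade 3 fasting glucose, where the dexamethasone-specific table recommends withholding it first.

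What is at stake is consistent handling of a steroid toxicity across approximately 30 sites, and a small safety margin for the subject. Dexamethasone exposure and relative dose intensity are summarized descriptively (SAP Section 9.6.7 and Appendix A), so differences in practice between sites would show there.

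**Working it through.** **The texts side by side, Grade 3 dexamethasone-related hyperglycemia**

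| Drug | Section 9.2.2.3 | Table 11 | Conflict |
|---|---|---|---|
| Carfilzomib | need not be held | silent | none |
| Lenalidomide | need not be held | silent | none |
| Dexamethasone, initial hold | need not be held | hold until Grade 2 or lower | yes |
| Dexamethasone, initial dose reduction | not required | not recommended at the first step | none |

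Grade 4 is not in the 9.2.2.3 list, so no conflict arises there.

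**Which text governs**

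No sentence gives precedence, so this is an inference from four points:

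1. Section 9.2.2, the parent of 9.2.2.3, is headed as guidance for carfilzomib and lenalidomide.
2. Section 9.2.2.3 makes exceptions to the guidelines above it (Tables 7 to 9). Table 11 comes afterwards.
3. Table 9 footnote b routes toxicity likely due to dexamethasone to Table 11, and Section 9.2.3 names Table 11 as the dexamethasone guideline.
4. Table 11 sets its trigger at a Grade 3 glucose and its release at Grade 2 or lower. If 9.2.2.3 prevailed at Grade 3, both thresholds would lose their purpose.

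**Size per affected dose**

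Inputs: nominal dose 40 mg; Days 1, 8, 15 and 22 in Cycles 1-8; Days 1, 8 and 15 in Cycles 9-18 (Protocol Section 9.2.1.3, Tables 2 and 10).

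- Planned doses: 8 × 4 + 10 × 3 = 62. Planned course: 62 × 40 mg = 2480 mg.
- Dose given: 40 mg if 9.2.2.3 is followed; 0 mg at the first step of Table 11.
- One held dose, Cycles 1-8: 40 / 160 = 25.0% of the cycle.
- One held dose, Cycles 9-18: 40 / 120 = 33.3% of the cycle.
- One held dose over the course: 40 / 2480 = 1.6%.
- If Table 11's second step is reached from nominal dose, the dose is 20 mg, which removes 20 / 160 = 12.5% or 20 / 120 = 16.7% of the cycle, and 20 / 2480 = 0.8% of the course.

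If glucose recovers before the next scheduled dose, no dose differs.

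**Effect on dose evaluation**

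Section 5.4 requires at least 75% of planned dexamethasone doses for a subject without a DLT.

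- Cohorts 1-3 (Cycle 1, 4 doses): one hold leaves 3/4 = 75%, which passes; two leave 2/4 = 50%, which fails.
- Cohort 4 (Cycles 1-2, 8 doses): two holds leave 6/8 = 75%, which passes; three leave 5/8 = 62.5%, which fails.

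However, Section 5.2.1 does not exclude Grade 3 hyperglycemia attributable to dexamethasone from the DLT definition. A subject with a DLT who has received at least one carfilzomib dose is evaluable under Section 5.4 whether or not dexamethasone was held. The choice between the two texts should therefore not change the DLT denominator.

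**Whether dosing is still under way**

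The documents give planned durations, not actual dates. Counting from amendment 3 (13 December 2016) with the Section 5.7 figures: 12 months to enroll + 17 months on treatment + 4.5 months for transplant interruption = 33.5 months, or about late September 2019. The SAP amendment is dated 15 October 2019.

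**The case against.** The strongest reply is that both texts are advisory. Section 9.2.2.3 says a hold is not needed, and Table 11 is headed as a recommended action. A site that holds dexamethasone departs from neither, Section 9.2.3 follows on directly, and Table 9 already points to Table 11. All of that stands and keeps the matter minor. It does not remove the conflict, because a site that relies on 9.2.2.3 and doses at 40 mg departs from Table 11.

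A second reply is that the exception may be deliberate, with Table 11's row left to work at Grade 4. Intent is not stated, so this cannot be excluded outright. It fits poorly: Table 11 carries no matching exception, and its trigger and release thresholds are set around Grade 3.

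A third is that Grade 3 fatigue or gastrointestinal toxicity attributed to dexamethasone meets a similar overlap through Table 11's catch-all row. The overlap exists, but there a named exception stands against a residual row, and the two can be reconciled. Only hyperglycemia has two specific and opposite instructions.

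Two limits on consequence also stand. Table 11's trigger is a fasting value, while Section 10.1.6 requires no fasting sample and allows chemistry up to 72 hours before carfilzomib, so a routine panel result need not meet it. Table 11 is also not a ban on steroid at Grade 3, since its second step allows a reduced dose while glucose is uncontrolled.

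**Conclusion.** The inconsistency is real, sits in current text, and is minor. That the two instructions conflict is certain. That Table 11 should govern is a well-supported inference, and on that reading the word dexamethasone in the 9.2.2.3 lead-in is wrong for the hyperglycemia bullet.

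The per-dose and per-cycle sizes assume a subject still on the nominal 40 mg; one already reduced to 20 mg would go to 12 mg at the next decrement. The trial-wide effect cannot be estimated, because neither document gives a hyperglycemia frequency. A held dose would appear in the exposure tables, but no response, PFS, sample-size or cohort-opening result depends on it. On planned durations, few if any subjects would still have been on treatment by the date of the SAP amendment.

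**What to change.** In Section 9.2.2.3, replace the hyperglycemia bullet with:

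> Grade 3 dexamethasone-related hyperglycemia: carfilzomib and lenalidomide need not be held; for dexamethasone follow Table 11.

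Leave Table 11 and Section 5.2.1 unchanged. If any subject is still on treatment, send the line as a protocol clarification. If none is, record it as a note to file, which would help explain any site differences in dexamethasone holds and keep the wording out of later protocols. The cost is one line of text, with no new data, assessments or analyses.

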9.3 CONCOMITANT MEDICATIONS

A concomitant medication is defined as any prescription or over-the-counter preparation, including vitamins and supplements. All concomitant medications from signing of the informed consent until 30 days after the subject's last dose of study drug must be recorded on the electronic case report form (eCRF). Blood or blood products are not considered concomitant medications and must be recorded on the appropriate eCRF.

9.3.1 REQUIRED CONCOMITANT MEDICATIONS

Required prophylactic medications should be initiated at least 24 hours prior to the first administration of carfilzomib. Contraception must be in place at least 4 weeks prior to the first administration of carfilzomib and/or lenalidomide.

9.3.1.1 Antiviral Prophylaxis

Valacyclovir (or equivalent antiviral) is a required concomitant medication. Valacyclovir 500 mg orally, daily (or equivalent antiviral) should continue for the duration of treatment. Additional prophylaxis is at the investigator's discretion.

9.3.1.2 Anticoagulant Prophylaxis

Aspirin (or other anticoagulant or antiplatelet medication such as clopidogrel bisulfate, low-molecular-weight heparin, or warfarin), is a required concomitant medication while taking lenalidomide. In subjects with a prior history of deep vein thrombosis, low-molecular-weight heparin or therapeutic doses of warfarin (for a target international normalized ratio of 2–3) are required. Enteric-coated aspirin once-daily by mouth at the standard prophylactic dose should be administered for the duration of treatment with lenalidomide. Subjects with known high thrombotic risk, eg, prior deep vein thrombosis, should receive full anticoagulation at the investigator's discretion. Other antiplatelet or anticoagulation medications may be used in cases of intolerance to aspirin upon consultation with the sponsor study medical monitor.

9.3.1.3 Tumor Lysis Syndrome Prophylaxis

Allopurinol (or other approved uric acid-lowering agent) in subjects at high risk for tumor lysis syndrome (TLS) due to high tumor burden may be prescribed at the investigator's discretion. Allopurinol dose should be prescribed according to the package insert.

Subjects should be well hydrated ([Section 9.2](#)) to reduce the risk of TLS and decline in renal function; refer to the current Carfilzomib IB for safety guidance regarding TLS.

9.3.1.4 Contraception

Females of childbearing potential (FCBP) must:

- Avoid pregnancy for at least 4 weeks before beginning lenalidomide
- Have 2 negative pregnancy tests prior to starting treatment, the first, a serum pregnancy test within 10 to 14 days and the second, a urine or serum pregnancy test within 24 hours before dosing on Cycle 1 Day 1
- Pregnancy tests weekly for the first month of treatment
- Pregnancy tests monthly during treatment after the first month or semimonthly for women of childbearing potential with irregular menstruation
- Agree to abstain from heterosexual sexual intercourse or to use 2 methods of highly effective contraception beginning 4 weeks prior to initiating treatment with lenalidomide, during therapy, during dose interruptions and for 1 month following last dose of drug (more frequent pregnancy tests may be conducted if required per local regulations)

An FCBP is defined as a sexually mature female who: 1) has not undergone a hysterectomy or bilateral oophorectomy, or 2) has not been naturally postmenopausal for at least 24 consecutive months (ie, no menses at any time in the preceding 24 consecutive months). Amenorrhea following cancer therapy does not rule out childbearing potential.

Male subjects whose partners are FCBP must use 1 highly effective method of birth control plus 1 additional effective method of birth control (contraception) at the SAME TIME during treatment and for 3 months following the last dose of drug, unless they have undergone a medically-confirmed successful vasectomy. Male subjects must not donate sperm while taking study drugs and for 90 days after the last dose of study drugs.

Highly effective methods of contraception include:

- Intrauterine device (IUD)
- Hormonal therapy (birth control pills, injections, implants)
- Tubal ligation
- Vasectomy, with medical confirmation of success

Additional effective methods include:

- Latex condom
- Diaphragm
- Cervical Cap

9.3.2 OPTIONAL AND ALLOWED CONCOMITANT MEDICATIONS

Mycostatin or oral fluconazole to prevent oral thrush is optional and may be given at the investigator's discretion.

Subjects may receive antiemetics and antidiarrheal agents as necessary. Myeloid growth factors may be used if neutropenia occurs but should not be given prophylactically. Subjects may receive RBC transfusions, erythropoietic stimulating agents, or platelet transfusions if clinically indicated in accordance with institutional guidelines.

Palliative radiation for pain management is permitted with the written approval of the study medical monitor.

Bisphosphonates are permitted as indicated and in accordance with institutional guidelines.

9.3.3 EXCLUDED CONCOMITANT MEDICATIONS

Concurrent therapy with a marketed or investigational anticancer therapeutic or radiation to large marrow reserves for either a palliative or therapeutic intent is excluded. Long term (≥ 14 days) corticosteroids for nonmalignant conditions (eg, asthma, inflammatory bowel disease) equivalent to a dexamethasone dose > 4.0 mg/day or prednisone > 20 mg/day are not permitted (other than as indicated in this protocol). Higher steroid doses given short term for exacerbations of nonmalignant conditions (eg, asthma flare) are permitted with the approval

of the sponsor study medical monitor. Investigational agents are not to be used during the study.

Subjects requiring the use of excluded concomitant medications or procedures will be withdrawn from study treatment.

10 STUDY PROCEDURES

All protocol-required tests and observations, along with their chronology, are outlined in the Schedule of Assessments ([Appendix A](#)). On-study tests and observations are summarized below.

10.1 STUDY-SPECIFIC PROCEDURES

10.1.1 BASELINE PROCEDURES

To be completed prior to initiation of therapy:

- Skeletal survey (all subjects) ([Section 10.1.4.3](#))
- Beta-2 microglobulin ([Section 10.1.4.1](#))
- Plasmacytoma evaluation (if clinically indicated) ([Section 10.1.4.3](#))
- Bone marrow aspirate and biopsy (all subjects, [Section 10.1.4.2](#))

10.1.2 VITAL SIGNS

Vital signs will include pulse, blood pressure, respiratory rate, and temperature and will be assessed at Screening, prior to and after administration of carfilzomib on treatment days, and at EOT. Resting blood pressure readings will be taken before administration of carfilzomib on Days 1, 8, and 15 of each cycle. Pre-carfilzomib blood pressure may be assessed either before or after dexamethasone administration, and for a given patient should be done consistently before dexamethasone, or consistently after dexamethasone. The time of pre-carfilzomib dosing blood pressure assessment will be recorded. The time of Day 1, 8, and 15 dexamethasone administration will also be recorded (per report by patient if self-administered). During Cycles 1 through 6, 12, and 18, pre-carfilzomib blood pressure readings will be taken in triplicate. In addition to the predosing blood pressure assessments, postdosing resting blood pressure readings will be taken in triplicate on Days 1, 8, and 15 of

Cycles 1 through 6, 12, and 18. Postdosing blood pressure will be assessed from 10 to 60 minutes after completion of carfilzomib administration.

The subject should be in a supine position in a rested and calm state for at least 5 minutes before blood pressure assessments are conducted. If unable to be in a supine position, the subject should be in the most recumbent position possible. The position selected for a subject should be the same that is used throughout the study and documented on the vital sign CRF. The arm should be supported at the level of the heart. Every effort should be made to use the same instrument in measuring a subject's blood pressure throughout the study. When blood pressure measurements are taken in triplicate, readings should be taken a minute or more apart.

10.1.3 PHYSICAL EXAMINATION

A physical examination will be performed during Screening, on Day 1 of Cycles 2 through 18, and at the EOT. Physical exam will include:

- ECOG PS
- Examination of cardiovascular and respiratory systems
- Weight
- BSA (at Screening and on Day 1 of Cycles 2–18 only)
- Height (at Screening only)

Abnormal physical examination findings during Screening will be captured as medical history. Abnormal physical examination findings observed after signing of the informed consent will be recorded as AEs.

10.1.4 DISEASE ASSESSMENTS

10.1.4.1 Laboratory Evaluations of Disease Status

Laboratory assessments of disease status will be performed at Screening (within 21 days before dosing on Cycle 1 Day 1); at Day 1 (\pm 3 days) of Cycle 2 and each cycle thereafter; at the EOT; and every 8 weeks (every 56 ± 4 days) during Active Follow-up.

Disease assessments at Screening (within 21 days before dosing on Cycle 1 Day 1) or baseline, include the following:

- Serum protein electrophoresis (SPEP) with immunofixation
- Urine protein electrophoresis (UPEP; 24-hour assessment, no substitute method is acceptable) with immunofixation
- SFLC
- Quantitative immunoglobulins
- Beta-2 microglobulin

Disease assessments at Day 1 (\pm 3 days) of Cycle 2 and each cycle thereafter, at the EOT, and during Active Follow-up include the following:

- Serum protein electrophoresis (SPEP) with immunofixation
- UPEP with immunofixation
- SFLC
- Quantitative immunoglobulins

SPEP with immunofixation, UPEP with immunofixation, beta-2 microglobulin, SFLC, and quantitative immunoglobulin analyses will be performed at the local laboratory.

10.1.4.2 Bone Marrow Aspirate Assessments of Disease Status

A bone marrow aspirate is required at baseline, on Cycle 8 Day 1 (\pm 3 days), and to confirm a CR or sCR. An optional bone marrow aspirate may also be done upon progression of disease in subjects who consent to optional genomic biomarker studies. Details of aspirate sampling and shipment are described in the central laboratory manual.

At baseline, bone marrow aspirate will be evaluated by the local pathology lab to determine percent plasma cell involvement. For subjects whose aspirate is unobtainable, a bone marrow core biopsy should be obtained for quantification of percent plasma cell involvement. Bone marrow aspirate or biopsy samples (taken as part of standard of care) within 45 days prior to Cycle 1 Day 1 may be used to quantify percent plasma cell involvement.

Baseline bone marrow aspirate samples are also sent to the central laboratories for fluorescent in situ hybridization (FISH; [Section 10.2.3](#)) and for Next Generation Sequencing

(NGS) to allow MRD analysis ([Section 10.2.4](#)); also referred to herein as “MRD”). Subjects who consent to optional genomic biomarker evaluation will have the baseline genomic biomarker analyses performed on aspirate samples remaining after central FISH testing of baseline aspirate.

Bone marrow aspirate will be collected for central MRD analysis on Cycle 8 Day 1 for all subjects regardless of response status (\pm 2 days; see [Section 10.2.4](#)).

Subjects with laboratory evidence of CR require confirmatory bone marrow aspirate evaluation, by the central study laboratory, for MRD ([Section 10.2.4](#)), in addition to local bone marrow assessment for evaluation of CR per IMWG-URC ([Appendix C](#)).

Consenting subjects with PD may have a bone marrow aspirate done for optional genomic biomarker studies ([Section 10.2.5](#)).

In instances where sample availability is limited, samples for disease assessments take priority over those for correlative testing as specified in the laboratory manual.

